6.1.3 Post-Test

At the post-test visits, cognition-,CAP- and everyday function outcome measures will be re-administered by blinded Research Assistant Testers. Participants will complete the CAP, cognition, and everyday function measures administered at baseline. Alternative forms will be used, as available. The Tester will complete a form indicating whether or not they know the randomized condition of the participant to assess success of blinding and will confirm continued eligibility. A questionnaire will be administered to check for adverse events during the course of the study. Participants will be encouraged to complete post-test regardless of adherence. We will attempt to complete post test for up to 60 days after the training completion date (≥ 16 sessions completed) or 18 weeks post baseline if intervention was not attempted or completed. Participant post-tests will be conducted after the intervention phase for those who complete between 1-15 sessions.⁶

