 - **Telephone Search While Counting.** Participants search the telephone directory while counting strings of tones simultaneously. The recorded score is obtained by the combined performance on the Telephone Search and Telephone Search While Counting gives a measure of divided attention, as well as the scaled score. This subtest measures sustained attention¹¹⁷.

Exploratory measures

Exploratory measures include a measure of music aptitude and two self-efficacy measures.

Advanced Measures of Music Audiation (AMMA) consists of 30 paired piano melodies that is used to evaluate music aptitude¹¹⁸. Test-retest reliability for music majors is $r=.89$ and non-music majors, $r=.83$ ¹¹⁸.

The General Self-Efficacy¹¹⁹ is comprised of 23 positive and negative items on a 14-point Likert scale ranging from strongly disagree (1) to strongly agree (14). Internal reliability is established ($\alpha=.86-.71$). Items are designed to reflect elements of effort, initiation, and persistence as described in Bandura's social cognitive theory.

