Specific Aim 1: To examine the efficacy of piano training to improve CAP, cognition, and everyday function among older adults. We will compare changes in performance for piano training relative to control across the two measurement points (baseline, immediate post-test). We will use the PCA-derived composites of CAP and cognition, and everyday functioning as outcomes. We will use repeated measures analyses of variance within the mixed effects models, examining group as the between-subjects factor and time as the within-subjects factor. The group x time interaction will indicate whether the participants randomized to piano training change at differential rates over time relative to those randomized to the control group. This output will be obtained for each of the composite outcomes (CAP, cognition, and functional abilities). For aim 1 analyses and the composite outcomes of CAP, cognition, and everyday function, we will apply Holm-Bonferroni adjustments¹²⁵ to reduce Type I error. Specifically, the Holm-Bonferroni procedure uses a step-down process whereby p-values are sorted from lowest to highest, then the lowest p-value is used in its raw version, the second lowest p-value is multiplied by two, the third lowest p-value is multiplied by three and so on until the adjusted

p-value reaches or exceeds the pre-specified threshold for statistical significance, in our case a two-tailed p value of .05.

Intent-To-Treat Approach. We expect that some participants will not complete their intended followup according to the protocol for a variety of reasons, generating missing values. Intent-to-treat (ITT) analysis has become a widely accepted method for dealing with this issue. To maximize available information, we will employ statistical techniques that allow for the inclusion of missing data. Specifically, we will use linear mixed effects models to analyze data. This advanced analytical method allows for the inclusion of participants with missing data, so long as data are missing at random and offers flexibility with regard to the specification of the variance/covariance structure, which often leads to improved fit of the analytical model to the actual data. If there is non-ignorable missing data, we will apply pattern-mixture mixed effects models to assess the sensitivity of our findings with regard to missing data¹²⁶.

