Additional Analyses. To address exploratory aim 3, with identification of significant effects from the analyses for aim 1, we will examine behavioral mediators of interventions to determine mechanisms. We hypothesize that improved CAP will mediate cognitive gains. We hypothesize that cognitive gains will mediate functional gains. Formal mediation tests using a bootstrapping technique as outlined by Hayes¹²⁷ and Selig and Preacher¹²⁸ will be used to examine these hypotheses. The pre-to-post differences will be captured by a latent score¹²⁸, whereby the post-test score will serve as the outcome with pre-test score covaried. Results yield estimates and confidence intervals for the indirect and total effects. The procedure allows simultaneous estimation of all three pathways (M on Y; X on M; X on Y, where M=mediator (CAP score), Y=outcome (cognition), and X=predictor (group assignment)) as well as adjustment for covariates (e.g., depression). The use of bootstrapping will ensure that power is not reduced from the main effect analyses¹²⁹. An alpha of .05 will be used for these analyses.

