The randomized groups did not differ in sex, $\chi^2(1)=.787, p=.375$, ethnicity $\chi^2(1)=.167, p=.683$, or race, $\chi^2(1)=.045, p=.832$. The Music Reading Assessment scores did not differ between the two groups, $t(266)=-.958, p=.338$. The randomized groups did not significantly differ in age, $F(1,266)=.293, p=.589$, education, $F(1,266)=.369, p=.544$, MoCA, $F(1,266)=.427, p=.514$, or GDS, $F(1,266)=.943, p=.332$. However, there were marginally significant group differences for PTA in the left ear, $F(1,266)=3.31, p=.070$ and statistically significant group differences for both PTA in the right ear, $F(1,266)=6.69, p=.010$, and visual acuity, $F(1,266)=8.99, p=.003$. The music listening group tended to have worse hearing, while the piano training group tended to have worse visual acuity. See Table 1. The groups also differed significantly in their expectations regarding potential benefits of their randomized group, $F(1,214)=15.07, p<.001$. The piano training group had an average rating of 5.55 while the music listening group had an average rating of 4.99, indicating the piano training condition had higher expectations about the potential effects of their randomized condition. The piano training group also rated their condition as more challenging with 92% agreeing that the intervention was challenging as compared to 86.3% of the music listening group indicating their condition was challenging ($p<.001$).

Principal component analysis with varimax rotation was conducted to reduce the number of variables for analyses. Please see Supplemental Table A for details. The first factor reflected cognitive performance speed and included the Trail Making Test, Digit Coding, and the TEA visual elevator and phone search subtests. The second factor included all three verbal fluency subtests. The third factor reflected CAP and included DDT, DSI, TCS, and WIN. The fourth factor included two indices from the TEA phone search while counting and visual elevator accuracy. The fifth composite included ATTR across- and within- channel performance. Baseline composites of cognitive performance, verbal fluency, ATTR, CAP, and everyday function were created by averaging z scores after the reverse-scaling of items with negative factor loadings. Post-test scores were standardized

by baseline means and *SDs*. Timed IADL performance did not significantly load on any factor and was thus examined separately.

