expectations about the assigned condition were significantly related to composite outcomes of CAP and cognition. However, having greater expectations that the randomized condition would positively affect abilities was associated with poorer performance. See Table 2. Additional sensitivity analyses examined if there were differential effects by sex. No significant group-time-sex interactions were evident ($p > .119$), and the pattern of results was the same when analyses were stratified by sex.

Table 14.1. *Participant characteristics by randomized arm and cognitive status.*

Cognitive status	Piano Training		Music Listening	
	Non-MCI	MCI	Non-MCI	MCI
	M (SD)	M (SD)	M (SD)	M (SD)
	n (%)	n (%)	n (%)	n (%)
Age in years	69.1 (5.5)	71.4 (7.1)	69.6 (5.2)	72.1 (5.7)
Education in years	16.0 (2.3)	16.5 (2.2)	16.0 (2.1)	15.4 (2.3)
Sex (% female)	63 (65%)	18 (48%)	58 (59%)	17 (44%)
Music Reading Assessment score (/40)	2.52 (4.31)	2.43 (3.83)	3.42 (5.41)	2.08 (4.29)
Montreal Cognitive Assessment score (/30)	26.6 (2.1)	23.3 (1.4)	26.6 (1.9)	22.8 (1.6)
Geriatric Depression Scale short-form score (/15)	0.9 (1.2)	1.1 (1.1)	0.9 (1.1)	0.6 (0.9)
Pure tone average left ear (dB)+	19.8 (9.4)	20.4 (9.4)	20.9 (10.8)	27.7 (15.9)
Pure tone average right ear (dB)+*	18.6 (10.3)	20.4 (9.9)	22.4 (14.0)	25.8 (11.6)
Visual acuity (logMAR)+*	.04 (.12)	.09 (.15)	.01 (.13)	.01 (.10)
Expectations (rating/7)*	5.4 (1.2)	5.8 (0.8)	4.9 (0.8)	5.3 (0.8)

Note. MCI=mild cognitive impairment. +Lower scores reflect better performance. *Significant differences by randomized group were evident in pure tone average right ear, visual acuity, and expectations ($ps<.01$).

Table 14.2. *The effects of randomization to piano training as compared to music listening from baseline to post-training across composite outcomes of central auditory processing, cognition, and everyday function.*

	Estimate	SE	p	Estimate	SE	p
	ATTR+			Central auditory processing		
Intercept	53.90	1.17	<.001	46.25	0.73	<.001
Group	-2.24	2.37	.346	-1.72	1.49	.249
Time	-2.77	0.68	<.001	2.29	0.36	<.001
Group x time	1.51	1.35	.265	.465	0.71	.515
Hearing	0.12	0.06	.030	-0.63	0.04	<.001
Visual acuity	6.24	4.71	.187	-7.270	3.97	0.07
Expectations	0.79	0.59	.185	-1.20	0.49	.016
	Verbal fluency			Cognition		
Intercept	49.32	0.98	<.001	51.81	0.90	<.001
Group	-1.81	2.00	.367	-2.62	1.84	.157
Time	0.41	0.48	.393	-1.40	0.42	.001
Group x time	-0.29	0.96	.763	0.39	0.84	.638

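### The exploratory mediation analysis in 9.6 is said to determine mechanisms, but it cannot separate a causal CAP effect from shared causes of CAP and cognitive change, or from reverse order

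*Combined protocol and SAP*

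**What the plan says.** Section 9.6, Additional Analyses, labels mediation as exploratory aim 3 and makes it conditional on significant aim 1 effects. It then says "we will examine behavioral mediators of interventions to determine mechanisms". The hypotheses are ordered: CAP gains should mediate cognitive gains, and cognitive gains should mediate functional gains. Change is represented by a model "whereby the post-test score will serve as the outcome with pre-test score covaried". Three paths are estimated (arm to mediator, mediator to outcome, arm to outcome), and the indirect effect gets a bootstrap interval. Covariates are allowed, with depression as the only example given there. On the error rate: "An alpha of .05 will be used for these analyses".

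Section 1.3 sets two measurement points, baseline and immediate post-test. Section 6.1.3 places all three domains in the same post-test: "Participants will complete the CAP, cognition, and everyday function measures administered at baseline". Section 9.7 plans sensitivity analyses for missing data and outliers only. Section 9.8 adds self-efficacy as a rival mediator. No section states that the mediation result depends on there being no unmeasured common cause of mediator and outcome.

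**The concern.** Randomisation protects the arm-to-CAP path and the total effect of arm on cognition. It does not protect the CAP-to-cognition path, because nobody is randomised to a CAP change. With both scores taken at the same two points, the order of the changes cannot be seen either. Anything that moves both scores between visits beyond what the baselines predict makes the CAP-to-cognition coefficient non-zero. Examples are form on the day, practice, or a general benefit of training that differs between people. Cognition driving performance on the CAP tests would do the same. The bootstrap shows how precisely the product of the two paths is estimated, not why it differs from zero.

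This matters because mediation is a listed secondary objective (1.2, 2.2) and CAP as the mechanism is the protocol's scientific premise (section 3). A significant interval would be read as confirming that premise.

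**Working it through.** **Inputs from the documents.** n=198, 99 per arm, f=0.10 and 95% power for aim 1 (9.3). Interim benchmark d=0.25 (6.3.4, 9.5). Alpha .05 for mediation, read as a 95% interval; aim 1 is two-sided ("in our case a two-tailed p value of .05"). No power or error rate is given for mediation.

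**Step 1: the plan's own figure.** For a group-by-time interaction with two groups and two times, the noncentrality is f²·N·m/(1−ρ), where m=2 and ρ is the pre-post correlation. With ρ=.70 this is 0.01×198×2/0.30 = 13.2, and power is 95.1%. The stated 95% therefore reproduces, but only with an unstated ρ near .70; at ρ=.50 power is 80.0%. In this design f=0.10 means a difference in change of 4×0.10 = 0.40 SD. The protocol's own gloss (f is about half of d) would give 0.20, so the results below cover 0.20 to 0.40 SD.

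**Step 2: what the indirect effect estimates when CAP has no causal role.** Let M1 = .7·M0 + a·X + e1 and Y1 = .7·Y0 + c·X + e2. X is arm, both residual SDs are √(1−.49) = 0.714, and corr(e1, e2) = r. Nothing runs from M to Y. Regressing Y1 on X, M1 and both baselines still gives a coefficient of r on M1, so the indirect effect is a·r. With a = c = 0.40 and r=.2 it is 0.08 SD, an apparent mediated share of 20%.

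**Step 3: simulation.** 600 trials per cell, 500 percentile-bootstrap resamples, both baselines covaried. Assumed: pre-post correlation .7, baseline CAP-cognition correlation .5, and r. *Gated* means that both CAP and cognition showed a favourable group-by-time effect at two-sided .05, without the Holm step. Entries are the share of trials whose 95% interval excluded zero.

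| Effect on CAP / cognition | Trials | r=0 | r=.1 | r=.2 | r=.3 | r=.4 |
|---|---|---|---|---|---|---|
| 0.40 / 0.40 SD | gated | 5% | 30% | 80% | 98% | 100% |
| 0.25 / 0.25 SD | gated | 3% | 24% | 73% | 92% | 90% |
| 0.20 / 0.20 SD | gated | 5% | 26% | 71% | 94% | 92% |
| 0.25 / 0.25 SD | all | 2% | 18% | 54% | 68% | 70% |
| 0 / 0.40 SD | all | 0% | 1% | 3% | 5% | 7% |

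Monte Carlo error is about 2 points for full cells and more for gated ones. With no CAP effect, too few trials pass both gates to give a gated rate. At most 2.8% of all trials in that row both passed and excluded zero.

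**Step 4: check by hand.** The standard error of the arm-to-CAP path is 2×0.714/√198 = 0.1015. Its power is Φ(0.25/0.1015 − 1.96) = 69% at 0.25 SD and Φ(0.40/0.1015 − 1.96) = 98% at 0.40 SD. Power for the CAP-to-cognition path is Φ(atanh(r)·√192 − 1.96): 28% at r=.1, 50% at .14, 80% at .2 and 99% at .3. At r=.2 the products are 0.69×0.80 = 55% (simulated 54%) and 0.98×0.80 = 78% (simulated 78%, ungated).

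**Step 5: the gate.** At 0.25 SD and r=.2 the rate is 54% ungated and 73% gated. Requiring a significant arm effect on CAP selects trials in which the first path is already established, so the rate moves towards that of the second path alone. Section 9.6 does not say which aim 1 outcomes must be significant.

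**Step 6: reverse order.** Suppose cognition moves by 0.40 SD, training has no direct effect on CAP, and 0.3 or 0.5 of the cognitive change carries into CAP (0.12 or 0.20 SD). A run of 400 ungated trials then declared mediation in 20% or 45%.

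**Step 7: where r might come from.** Unreliable baselines alone (reliability .7 to .9, latent correlation .3 to .7, all assumed) give a residual r of only .02 to .12. A value of .2 needs a shared source of change.

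**Step 8: cognition to function.** Section 14 reports that the first component "included the Trail Making Test, Digit Coding, and the TEA visual elevator and phone search subtests". The fourth component, used as the Test of Everyday Attention (TEA) composite, includes indices from Telephone Search While Counting. Section 6.3.5 says of that subtest: "The recorded score is obtained by the combined performance on the Telephone Search and Telephone Search While Counting". Telephone Search therefore enters both sides of this mediation model.

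**The case against.** The analysis is exploratory and gated. It covaries the pre-test, includes arm and requires an arm effect on the mediator, so it is not a plain correlation of post-test scores. Its bootstrap holds about 5% when there is no residual correlation. Self-efficacy is planned as a rival mediator. The limitation is common to any trial with a randomised treatment and a concurrently measured mediator. All of this is correct, and it limits the point without removing it: the gate does not lower the rate, and the plan states a causal purpose without the assumption that purpose needs.

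Some stronger readings are tempting, and the documents do not support them.

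- A reader might infer that the test will usually declare a mechanism falsely. That needs a real training effect on CAP and r above about .14. The documents give no r.
- Section 14 says that "expectations about the assigned condition were significantly related to composite outcomes of CAP and cognition", and hearing also relates to both. A reader might take this as proof of a residual correlation. Those coefficients are main effects pooled over both visits, not effects on change. Section 9.6 already makes hearing and expectations covariates when the arms differ at p<.1.
- The Telephone Search overlap might be taken to inflate mediation. Its direction is not shown. Table 14.3 names a dual-task decrement. If that is a difference score, slow Telephone Search would worsen cognition but shrink the decrement. Timed IADL, examined separately, is unaffected.
- Baseline adjustment might be thought to cure the problem. The rates above already include both baselines. Leaving baseline CAP out of the cognition equation gave lower gated rates at r=.2 (51% at 0.25 SD, 58% at 0.40 SD).

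**Conclusion.** The point holds as a limit on what may be concluded. As planned, the mediation analysis cannot distinguish a causal CAP effect from shared causes or reverse order. If training moves CAP and cognition by 0.25 to 0.40 SD and r is about .2 or more, mediation would be declared in roughly 70% or more of gated trials with no causal CAP role. The error largely disappears when r is near zero or training does not move CAP. These rates rest on the assumed pre-post correlation, baseline correlation and r, and on the simulated form of the gate.

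This is a weakness of the plan, not a demonstrated false claim. Section 14 reports no significant group-by-time interaction for any outcome (all p above .194), so the gate was not met, and it gives no mediation result.

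**What to change.** In 9.6, Additional Analyses:

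1. Replace the stated aim of determining mechanisms. Say that a significant indirect effect is consistent with mediation, conditional on no unmeasured mediator-outcome confounding and on the assumed order of change.
2. With each indirect effect, report a sensitivity analysis over the residual correlation between the mediator and outcome equations, and give the value at which the indirect effect reaches zero. In the linear model with the same covariates in both equations, this is the correlation between the residuals of mediator and outcome after each is regressed on arm and those covariates. Set no fixed survival threshold, because the documents offer no basis for one.
3. For cognition to function with the TEA composite, repeat the analysis with Telephone Search removed from one composite, as a sensitivity check.

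No new data are needed. The cost is some wording, a little extra analysis, and a weaker claim from any positive result.

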2.2 Secondary Objectives

The secondary objectives are:

- To examine the moderating effects of MCI on piano training efficacy. Moderating effects of MCI status will determine if piano training is effective for older adults with and/or without MCI.

Rationale: It is possible that piano training is effective prior to cognitive decline, but not in those with MCI. It is also possible that cognitive and/or functional abilities may be differentially enhanced among those with and without MCI. Delineating the effects of piano training among those with and without MCI will discern who is most likely to benefit from piano training, and for what specific outcomes. We do not have a directional hypothesis for this objective.

- To explore mediators of intervention effects.

Hypothesis: Grounded in theory⁸ and prior research⁹⁻¹¹, we hypothesize that piano training will improve CAP and cognitive performance, leading to functional improvements. We expect that enhanced CAP will mediate cognitive gains. We further hypothesize that cognitive gains will mediate functional improvements.

Rationale: Crucially, we must discern the underlying mechanisms of effective interventions in order to maximize training gains.

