9.3 Sample Size

We expect up to 20% attrition after the initial in-person visit across the time period in which cognitive intervention study protocols will be administered. Our goal is to complete in-person screening visits for up to 450 participants in order to have up to 360 participants complete the study. We can tolerate higher rates of attrition. We require a minimum of 198 eligible participants with *at least* 99 individuals randomized to each condition (piano training, controls) to have adequate statistical power. With stratified randomization, this will result in *at least* 48 persons per MCI/no MCI subgroup.

Statistical power analysis using G*Power¹²³ in consideration of our pilot data effect sizes as well as attrition was conducted to estimate power. We will control type I error at .05 to achieve at least 80% statistical power.

To power **Specific Aim 1: To examine the efficacy of piano training to improve CAP, cognition, and everyday function among older adults**, a final n of 198 participants ($n=99$ per randomized condition) will achieve 95% power to detect a significant group x time interaction across baseline to immediate post-test, with an alpha of .05. This assumes a small effect size (f) of 0.10¹²⁴ (Cohen's f effect sizes are 0.10- small, 0.25- medium: f is roughly equivalent to $\frac{1}{2}$ of d when comparing two groups)¹²⁴.

To power **Specific Aim 2: To examine the moderating effects of MCI on intervention efficacy**, a final n of 168 will have .95 power at alpha .05 to detect medium effects ($f=.10$) for significant group x time x moderator three way interactions.

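### Bootstrapping cannot guarantee that the mediation test keeps the power of the main-effect analyses; that power depends on both mediation paths and on n

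*Combined protocol and SAP*

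**What the plan says.** Section 9.6, Additional Analyses, plans bootstrap mediation tests with group as predictor, CAP as mediator and cognition as outcome. The post-test score is modelled with the pre-test score as covariate. The section then asserts "The use of bootstrapping will ensure that power is not reduced from the main effect analyses" and adds "An alpha of .05 will be used for these analyses". Estimates and confidence intervals for the indirect and total effects are already promised. The analysis is labelled exploratory and follows only if Aim 1 shows significant effects.

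Section 9.3 gives power for Aims 1 and 2 only. For Aim 1, 198 participants "will achieve 95% power to detect a significant group x time interaction across baseline to immediate post-test, with an alpha of .05", assuming f = 0.10. The sample size is a range: the floor is "We require a minimum of 198 eligible participants with *at least* 99 individuals randomized to each condition", and the goal is to screen up to 450 "in order to have up to 360 participants complete the study". No path values, pre-post correlation or mediation power calculation appear. The section 9.6 sentence is therefore the plan's only statement about mediation power.

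**The concern.** A bootstrap gives an interval for a product of two coefficients that need not be symmetric. It adds no information. To detect the indirect effect, the data must support both the effect of training on CAP and the association of CAP with cognition given group. Neither is fixed by the size of the total effect on cognition, so no choice of resampling method can tie one power to the other.

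Mechanism is central to the rationale: section 2.2 says "we must discern the underlying mechanisms of effective interventions in order to maximize training gains". The plan has no rule for an indirect-effect interval that covers zero. A reader who accepts the sentence could carry main-effect power over to the mediation test and take a null result as evidence against CAP, when the test may have been weak.

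**Working it through.** **1. The plan's own figure.** For the group x time interaction with two groups and two times, the noncentrality is lambda = f² x N x 2 / (1 - rho), with 1 and 196 df. The pre-post correlation rho is not stated.

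- rho = 0.70: lambda = 0.01 x 198 x 2 / 0.30 = 13.2, power 0.951.
- rho = 0.50: lambda = 7.92, power 0.800.

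The stated 95% therefore reproduces with rho of about 0.70. A noncentrality of 13.2 corresponds to a standardised group difference of sqrt(4 x 13.2 / 198) = 0.516, used below for the total effect.

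**2. Assumptions for the mediation test.** Scores are baseline-adjusted with unit residual variance, allocation is 1:1 and tests are two-sided at .05 (section 9.6: "in our case a two-tailed p value of .05" for Aim 1; a 95% interval is assumed for mediation). Here a is the group effect on CAP in SD units and b is the standardised CAP-to-cognition path. Both are assumed.

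**3. Analytic approximation.** Indirect-effect power is about power(a) x power(b), with noncentralities a x sqrt(n/4) and b x sqrt(n).

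For n = 198 and a = 0.516: 0.516 x 7.036 = 3.63, so power(a) = 0.951. For b = .10: .10 x 14.07 = 1.41, so power(b) = 0.288, and the product is 0.951 x 0.288 = 0.274.

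| n | a | power(a) | b = .10 | b = .15 | b = .20 | b = .30 | b = .50 |
|---|---|---|---|---|---|---|---|
| 198 | .516 | .951 | .27 | .53 | .76 | .94 | .95 |
| 198 | .40 | .800 | .23 | .44 | .64 | .79 | .80 |
| 198 | .28 | .500 | .14 | .28 | .40 | .49 | .50 |
| 360 | .516 | .998 | .47 | .81 | .96 | 1.00 | 1.00 |
| 360 | .28 | .755 | .36 | .61 | .73 | .76 | .76 |

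**4. Check by simulation.** Percentile-bootstrap simulations with the total effect held at about 95% power for n = 198 agree. With the stronger a-path (.51 to .52), repeated runs gave 22-27%, 52-57%, 75-77% and 93-95% for b = .10, .15, .20 and .30. With a = .28 they gave 37% at b = .20 and about 50% at b = .50. At n = 360 with a = .516 they gave 48% at b = .10, 77% at b = .14 and 97% at b = .20, against total-effect power above 99%.

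**5. Does the Aim 1 gate restore power?** No. Among simulated trials with a significant total effect (n = 198, a about .52), indirect-effect power was 26% at b = .10 and 49% at b = .14, almost unchanged.

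**6. The opposite case.** With full mediation, n = 198 and a = b = .39, the total effect is .39 x .39 = .152. Simulated power was 79% for the indirect effect and 18% for the total effect.

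**The case against.** The strongest reply is that the low figures describe cases in which CAP is barely the mechanism. With a equal to the total effect, b = .10 or .15 means CAP carries 10% or 15% of the benefit, and doubting CAP as the main mechanism would then be broadly right. The plan's premise is that CAP matters much more. With a strong training-to-CAP path and b of .30 or more, the loss essentially disappears, and under full mediation the order reverses.

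This stands as a limit on size. It does not rescue the guarantee. With a = .28 and b = .50, CAP carries .28 x .50 / .516 = 27% of the effect, and power at n = 198 is still about 50%.

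Three stronger readings are tempting, and the documents support none of them:

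- *Mediation power is generally a quarter to a half of main-effect power.* This needs the minimum n and a weak path. At 360 completers the quarter disappears in the cases examined.
- *The plan claims 95% power for mediation.* Section 9.3 attaches that figure only to the Aim 1 and Aim 2 interactions.
- *A null mediation result would be misread.* No passage says that a null refutes the mechanism. Section 14 reports no significant group-by-time interaction, so the gate was not met, and no mediation result is reported.

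Aim 1 also carries a Holm-Bonferroni adjustment. At .05/3 and rho = 0.70 its power is 0.887, which narrows the gap slightly.

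**Conclusion.** The sentence is wrong as an unconditional guarantee. Indirect-effect power may be far below, similar to or above total-effect power, depending on two paths the plan does not specify. The worked range at n = 198 runs from 14% (a = .28, b = .10) to about 95% (a = .516, b of .30 or more), with total-effect power near 95% throughout.

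These figures rest on assumed path values, unit residual variance, the stated total-effect power and 198 participants analysed. Section 9.3 calls 198 the final n, and Table 14.3 reports an overall analytic sample of that size. The conclusion that the guarantee fails does not depend on any particular path value.

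The consequence is small. The analysis is exploratory and gated, sets no sample size or primary test, and already has interval reporting planned. A null mediation result could be misread; the documents do not show that it would be.

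**What to change.** In section 9.6, delete the sentence and replace it with three statements:

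1. Mediation power is not guaranteed by the bootstrap or by the Aim 1 sample size.
2. Indirect-effect power is given over a stated grid of training-to-CAP and CAP-to-cognition paths at n = 198 and n = 360, with the pre-post correlation behind the Aim 1 figure stated.
3. An indirect-effect interval that covers zero is inconclusive and is not evidence against CAP as a mechanism.

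The promised estimates and intervals need no change. The cost is a few lines of SAP text and a less favourable statement of power, with no change to design, data collection or the primary analysis.
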